Quantitative research assistants will conduct the phone follow-up interviews using an EDC mobile application. Personally identifiable information (PII) will be used for contacting caregivers. No time window applies to Day 7 follow-up. A window of +7 days applies to Day 28 phone call attempts (Day 28 to Day 35).

Data that will be collected at Day 7 follow-up will include cure status (recovery from illness as reported by the caregiver), death and hospitalization information between Day 0 and Day 7 as

reported by caregivers. The primary outcomes on the proportion of children with severe complications by Day 7 and on the proportion of children admitted to hospital within 24 hours of the Day 0 primary care consultation as a result of a referral will be assessed based on Day 7 follow-up. Hospital name, duration of hospitalization and reason for admission will be collected for children reported to have been hospitalized to facilitate the retrospective data collection at referral hospital level.

Data collected at Day 28 follow-up will include death and hospitalization information as reported by the caregiver. The secondary outcome on the proportion of children with severe complications at Day 28 will be assessed on the basis of this interview.

Higher level of care visit

Data collection will be conducted retrospectively at all government-designated and private referral facilities within the study area, including hospitals or emergency / inpatient area of larger primary or secondary care facilities (e.g., study facilities that can admit paediatric patients). A quantitative research assistant using the EDC mobile application will collect data from referral facility records, registries and discharge summaries to document hospitalization for all children reported to have been hospitalized between Day 0 and Day 7. Personally identifiable information will be collected to cross-check the identity of the patients. Arrival date and time, basic clinical information on arrival and, if admitted, admission and discharge diagnosis, and admission duration and outcome will be collected. If available, data on oxygen saturation at admission, oxygen administration and intensive care unit (ICU) admission and duration will also be recorded.

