3.8 Timing for Baseline and Outcome Assessments

Baseline is defined as the date of enrolment (Day 0) and time will be measured from this point.

Follow-up will occur 7 days and 28 days after Day 0. As defined in the protocol, no time window applies to Day 7 follow-up and a window of + 7 days applies to Day 28 follow-up. Refer to “Participants timeline” section of the protocol for more details.

The components (i.e. death and hospitalisation) required for the analysis of the primary outcomes will be assessed at both Day 7 and Day 28 follow-ups. For the main analysis, date of death and date of hospitalisation will be used irrespective of when these information are collected.

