6.1.1 General definitions

Day 7 / Day 28 assessment

Day 7 / Day 28 assessment refers to information reported by the caregiver after Day 0 and recorded in Day 7 / Day 28 forms. Data collected as part of unscheduled visits are also integrated in these forms.

If multiple successful follow-up assessments for the same child are recorded within Day7 or Day28 databases, the most recent follow-up assessment within each database will be used. To limit potential recall bias, assessments conducted far beyond the expected follow-up time will be dropped. This will be 30 and 60 days from Day 0 for Day 7 and Day 28 respectively.

Death

A child will be considered deceased if, from Day 7 / Day 28 assessment, his/her status at the time of follow-up is “deceased”. In case of implausible death date (i.e. prior to enrolment date), death will be handled as follow:

- ξ if death date is recorded at Day7 follow-up, death will be assumed to be within 7 days of Day0
- ξ if death date is not recorded at Day7 follow-up but only at Day28 follow-up, death will be assumed to be after 7 days of Day0 but within 28 days.

Hospitalisation

A child will be considered hospitalised if, from Day 7 / Day 28 assessment, he/she went to a hospital, was admitted overnight or if his/her status at the time of follow-up is “hospitalised”. In case of implausible hospitalisation date (i.e. prior to enrolment date), hospitalisation will be handled as follow:

- ξ if hospitalisation date is recorded at Day7 follow-up, hospitalisation will be assumed to be within 7 days but after 24hrs of Day0
- ξ if hospitalisation date is not recorded at Day7 follow-up but only at Day28 follow-up, hospitalisation will be assumed to be after 7 days of Day0 but within 28 days.

Hospitalisation within 24hrs of Day0

For the purpose of primary analysis, a child will be considered admitted to hospital 24hrs of Day0 consultation if the date of hospitalisation is the same as Day0 date or is one day after Day0 date.

Referral

A child will be considered to be referred (either to a hospital or to an inpatient part of a larger primary healthcare facility) if, at Day0, the caregiver confirms that the child was urgently referred or the research assistant confirms that an urgent referral advice was recorded for the child. If urgency is unknown from both sources, referral will be assumed to be urgent.¹

Antibiotics

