6.1.2 Health, hospitalisation and referral outcomes

6.1.2.1 Proportion of children with a severe complication by Day 7

Severe complication is defined as death or secondary hospitalisation. Secondary hospitalisation refers to any delayed hospitalisation (occurring at any point greater than 24hrs after the Day 0 consultation) and any hospitalisation occurring without a referral.

Information on death and hospitalisation will be taken, in order, from:

- ξ Day7 follow-up assessment
- ξ If Day7 follow-up assessment is missing, Day28 follow-up assessment

Death will be counted in the numerator if death date is within 7 days of Day0 (7th day included). Hospitalisation will be counted in the numerator if the child was not referred at Day0 or hospital admission date is within 7 days of Day0 (7th day included) but after 24hrs of Day0.

The denominator will be all children recruited. Children for whom no death and hospitalisation data are available or withdrew prematurely from the study will be assumed to be alive and not hospitalised by Day7.

6.1.2.2 Proportion of children with a severe complication by Day 28

Severe complication is defined as per the outcome above.

Information on death and hospitalisation will be taken, in order, from:

- ξ Day7 follow-up assessment
- ξ If Day7 follow-up assessment is missing or no outcomes were reported, Day28 follow-up assessment
- ξ If both Day7 and Day28 assessments are missing or no outcomes were reported, unscheduled visits (deaths only)

Death will be counted in the numerator if death date is within 28 days of Day0 (28th day included). Hospitalisation will be counted in the numerator if the child was not referred at Day0 or hospital admission date is within 28 days of Day0 (28th day included) but after 24hrs of Day0.

The denominator will be all children recruited. Children for whom no death and hospitalisation data are available or withdrew prematurely from the study will be assumed to be alive and not hospitalised by Day28.

6.1.2.3 Proportion of children admitted to hospital within 24 hours of Day 0 consultation and as a result of a referral

Information on hospitalisation will be taken, in order, from:

- ξ Day7 follow-up assessment
- ξ If Day7 follow-up assessment is missing, Day28 follow-up assessment

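### The SAP's Day 30 and Day 60 cut-offs discard dated deaths along with the rest of a late form, and the Day 7 and Day 28 outcomes list different sources for deaths

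*SAP*

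**What the plan says.** On late forms, SAP 6.1.1 gives recall bias as its reason and states that "assessments conducted far beyond the expected follow-up time will be dropped. This will be 30 and 60 days from Day 0 for Day 7 and" (the 60 is for Day 28). The unit dropped is the whole assessment. The definition of death in the same section rests on the Day 7 and Day 28 assessments.

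On timing, SAP 3.8 states: "For the main analysis, date of death and date of hospitalisation will be used irrespective of when these information are collected". It also says that "no time window applies to Day 7 follow-up and a window of + 7 days applies to Day 28 follow-up". Protocol 8.1.1 agrees: "No time window applies to Day 7 follow-up".

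On sources, SAP 6.1.2.1 (severe complication by Day 7) uses the Day 7 form and, if that is missing, the Day 28 form. If neither gives data, the child is taken to be alive and not hospitalised, and SAP 6.3 makes this best case the primary rule for losses. SAP 6.1.2.2 (the Day 28 version) adds a third source: "If both Day7 and Day28 assessments are missing or no outcomes were reported, unscheduled visits (deaths only". Yet SAP 6.1.1 says that unscheduled-visit data are already integrated in the Day 7 and Day 28 forms.

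**The concern.** One section tells the analyst to use the event date whenever it was learned, and another tells them to discard the form that carries it. Best-case scoring then turns the discarded report into a survivor. The stated reason is recall bias, but a caregiver is much less likely to misreport that a child died than to misreport symptoms or recovery. The rule does not track recall length either: a Day 28 form completed on Day 59 is accepted as the fallback for the Day 7 outcome, while a Day 7 form completed on Day 35 is not.

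The unequal source lists raise a second question. If integration of unscheduled visits were complete, the third source in 6.1.2.2 would be redundant. If it is not complete, one child can be a severe complication by Day 28 but not by Day 7, although the death occurred on Day 3.

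At stake are the death component of a primary outcome and the agreement between the Day 7 and Day 28 results.

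**Working it through.** **Applying the rules to a death on Day 3**

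| How the death is learned | Day 7 outcome as written |
|---|---|
| Day 7 form on Day 35, no usable Day 28 form | Form dropped; child scored alive and not hospitalised |
| Day 28 form on Day 35, no Day 7 form | Kept; death counted by its date |
| Day 7 form on Day 35, and a Day 28 form by Day 60 that reports it | Day 7 form dropped; death recovered from the Day 28 form |
| Unscheduled visit only, both forms missing | Counted by Day 28 (6.1.2.2); not by Day 7 (6.1.2.1), unless the integration sentence in 6.1.1 covers it |

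The first two rows have the same event, date and reporting day. Only the form label differs.

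**Reproducing the plan's sample size, for scale**

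Inputs (Protocol 1 Summary; SAP 3.4): 1.1% versus 0.77%, power 80%, alpha 0.05 (two-sided assumed), ICC 0.001.

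- n = [1.960·√(2·0.00935·0.99065) + 0.842·√(0.011·0.989 + 0.0077·0.9923)]² / 0.0033² = 13,351 per arm before clustering.
- India, initial design: design effect 1 + 509 × 0.001 = 1.509; 13,351 × 1.509 = 20,147, or 39.5 clusters of 510. Rounded up to 40, this is the stated 20,400.
- Tanzania: design effect 1 + 1,679 × 0.001 = 2.679; 13,351 × 2.679 = 35,767, or 21.3 clusters of 1,680. Rounded up to 22, this is the stated 36,960.

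The plan's figures reproduce, and nothing here changes them.

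**How many events might be affected**

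India after reallocation is taken as 60 × 510 = 30,600 per arm, assuming all 60 facilities are used and the average of 510 holds.

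- Expected control-arm composite events: 1.1% × 30,600 = 337 (India); 1.1% × 36,960 = 407 (Tanzania).
- Assumed mortality of 0.1% (not in the documents): 31 and 37 deaths per arm.
- Assumed 5 to 10% of deaths learned only by the affected routes (not in the documents): 5% × 31 = 1.5 to 10% × 37 = 3.7, so about 2 to 4 per arm.
- Share of composite events: 2/407 = 0.5% to 4/337 = 1.2%.
- Ceiling: at 0.1% mortality, deaths are 0.1/1.1 = 9.1% of composite events, so losing every death could not exceed that share.

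**Effect on the primary comparison**

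Let f be the share of composite events rescored as non-events. With equal loss, both rates are multiplied by (1 − f) and power is recomputed on the effective sample (36,960/2.679 = 13,796; 30,600/1.509 = 20,278).

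| f | Power, Tanzania | Power, India (60 clusters per arm) |
|---|---|---|
| 0 | 81.3% | 93.2% |
| 1% | 80.9% | 93.0% |
| 5% | 79.3% | 92.0% |
| 10% | 77.1% | 90.6% |

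The 2 to 4 deaths assumed above correspond to f of about 1%. If all of a 1% loss fell in one arm, the planned risk ratio of 0.70 would become 0.0077/(0.011 × 0.99) = 0.707 (control only) or 0.0077 × 0.99/0.011 = 0.693 (intervention only).

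**The case against.** **SAP 3.8 can be read more narrowly.** The sentence before the one on event dates says that both follow-ups assess death and hospitalisation, so the rule may only mean whichever of the two forms reported the event. Section 6.1.1 would then be a specific rule refining a general one. This softens the clash over event dates. It does not explain why Day 7 follow-up has no window yet forms expire at Day 30, or why the form label decides the outcome.

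**The loss needs two failures.** A reader might infer that any late Day 7 form loses a death. It does not: Day 28 follow-up is attempted even when Day 7 fails, and that form is usable to Day 60. Nor do the documents show that Day 7 forms after Day 30 are common. Protocol 6.5.1 puts the repeat calls on the next three days and in-person visits as soon as possible after that. The Day 60 cut is itself more lenient than the protocol's Day 28 to Day 35 call window. All of this stands.

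**Unscheduled visits.** A reader might infer that the Day 7 outcome ignores deaths known from these visits. The integration sentence in 6.1.1 prevents that conclusion; what is established is an inconsistency between sections.

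**Size and direction.** Two deaths are 5.4% of 37 or 6.5% of 31, and a reader might carry that shift over to the primary outcome. The outcome is a composite, so the relevant share is about 1%. An imbalance between arms also has no stated mechanism: the rule is the same in every arm, and Protocol 7.2 has outcome callers blinded.

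**Harm counts.** SAP 6.5 counts deaths over the whole study without invoking the cut-offs, so the documents do not show that harm counts are affected.

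**Hospitalisation differs from death.** An admission after a referral counts towards one primary outcome if dated Day 0 or the next day, and towards the other if later within the week. A recalled date therefore decides which is met, and the recall argument for the cut has force there.

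**Conclusion.** The point holds in limited form. As written, SAP 6.1.1 can discard a death that the trial has on record with a date inside the window, and SAP 6.1.2.1 and 6.3 then score that child as alive. This needs a Day 7 form after Day 30 and no usable Day 28 form. The death sources for the Day 7 and Day 28 outcomes also differ in a way the text does not resolve.

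The frequency is unknown and probably low. Under the assumed 0.1% mortality and 5 to 10% late discovery, about 0.5 to 1.2% of composite events per arm are affected, and power falls by less than half a percentage point if the loss is equal across arms. The case for correction rests on the death component and on internal consistency, not on a threat to the main result.

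The planned sensitivity analyses do not repair it. The complete-case analysis (SAP 4.3, planned whatever the amount of missing data) and multiple imputation do not use the discarded report. Worst case counts every lost child as an event. The missing-data set in SAP 6.2.4 is triggered only by substantial missingness, with above 10% given as the example.

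**What to change.** 1. In SAP 6.1.1, state that a death with a plausible date is kept from any form, whenever completed, and classified by that date in line with SAP 3.8. Limit the Day 30 and Day 60 cut-offs to recall-dependent items.
2. In SAP 6.1.2.1, add unscheduled visits (deaths only) as the last source, in the same words as 6.1.2.2.
3. For hospitalisation, keep the cut-offs in the main analysis, or show late-reported admissions in a sensitivity analysis.
4. Add a sensitivity analysis that applies the Day 30 and Day 60 cut-offs to deaths as well.

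The cost is a few sentences in the SAP and no new data. The downside is that a few deaths will be dated with longer recall, which the analysis in item 4 would show.

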6.4.2 Pragmatic cluster RCT

Two primary outcomes will be assessed in order to improve the ability to detect a difference between intervention and control arms, given the relatively low occurrence of severe outcomes at primary care level:

- Proportion of children with a severe complication (death or secondary hospitalisation) by Day 7
 - Secondary hospitalisation refers to any delayed hospitalisation (occurring at any point greater than 24 hours after Day 0 consultation) and any hospitalisation occurring without referral. The denominator is all enrolled children

- Proportion of children admitted to hospital within 24 hours of the Day 0 primary care consultation and as a result of a referral
 - This is used as a proxy for 'appropriate referral' of children, as those with severe disease should generally be admitted to hospital. The denominator for this outcome is also all children enrolled in the study, rather than only referred children. This is because the proportion of referred children that are admitted may be high in routine care, in the context of an inappropriately low referral rate. The aim of the intervention is therefore to increase the overall referral rate of children with severe disease. Hospital admission is chosen as the proxy of severe disease rather than using primary care classification of severe disease, as there are inadequacies in the classification of severe disease in routine practice

The trial will be interpreted as positive if either primary outcome is positive with no indication of harm from non-significant outcomes. This will be assessed separately in India and Tanzania and will also be assessed across the two countries for the sub-group of children presenting with cough or difficulty breathing.

We anticipate that we will see a greater effect on the 'appropriate referral' outcome, given that increasing detection and referral of children with severe disease is the focus of the intervention, and that morbidity and mortality among children with severe disease is highly contingent on quality of care at hospital level, which is not the focus of the intervention. Whilst hospital admission is still contingent on factors beyond the remit of the intervention (e.g. on caregiver completion of referral and hospital bed availability), it is not dependent on quality of care during hospital admission.

Secondary outcomes:

- Proportion of children with severe complication (death or secondary hospitalisation) by Day 28

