- Proportion of children cured (defined as caregiver reported recovery from illness) at Day 7 follow-up
- Proportion of children referred by a primary care healthcare provider to a higher level of care (either to a hospital or to an inpatient part of a larger primary healthcare facility) at Day 0 consultation

Proportion of children who completed referral, as reported at day 7 follow-up
Other outcomes of interest – hypoxaemia (in intervention arms only)

- Proportion of children with severe ($\text{SpO}_2 < 90\%$), moderate ($\text{SpO}_2 90 - 91\%$) and mild hypoxaemia ($\text{SpO}_2 92 - 93\%$), adjusted for sites at high altitude
- Proportion of children with hypoxaemia (according to differing cut-offs) with severe complication
- Proportion of children with severe hypoxaemia not meeting any other clinical criteria for severe disease

- Proportion of children referred with hypoxaemia who receive oxygen at hospital

Other outcomes of interest – referral and follow-up

- Proportion of children with non-severe disease referred to a higher level of care on Day 0
- Average length of stay (in days) of children admitted to hospital
- Proportion of children attending scheduled follow-up at the same facility by Day 7
- Proportion of children presenting for unscheduled follow-up to any health facility by Day 7

Other outcomes of interest – antimicrobial prescription

- Proportion of children prescribed an antibiotic at Day 0
- Proportion of children prescribed a diagnosis-appropriate antibiotic
- Proportion of febrile children tested for malaria at Day 0
- Proportion of malaria positive children prescribed an antimalarial
- Proportion of malaria negative children prescribed an antimalarial
- Proportion of untested children prescribed an antimalarial

Sub-groups for analysis of primary and secondary outcomes:

- Age (under 2 months, 2 – 12 months, 13 – 59 months)
- Sex
- Presentation with cough / difficulty breathing

Other factors for exploratory analyses

- Additional sociodemographic characteristics urban / rural location, distance from health facility, key household indicators such as maternal age and education
- Main complaint / symptom categories (including cough / difficulty breathing, fever, diarrhoea and other) and time since onset of symptoms
- Alternative hypoxaemia cut-offs
- Healthcare provider severity classification
- Facility and health system factors – type of facility, healthcare provider qualification and previous training

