Antibiotics will be defined in accordance with the WHO antibiotic point prevalence survey (PPS) methodology [7, 8, 9] and therefore only antibacterials for systemic use will be taken into account.

¹ Urgency, as reported by the caregiver, was only collected in Tanzania. For India, urgent referrals will be defined based on the registry alone.

SpO₂ values

SpO₂ should be recorded during the Day0. For the outcomes, the following measures will be taken for spurious and missing SpO₂ values:

- If SpO₂ value is not available, the child will be assumed normoxaemic
- If $70 \leq \text{SpO}_2 < 90\%$, the child will be assumed (with accuracy) to have severe hypoxaemia
- If $40 \leq \text{SpO}_2 < 70\%$, the child will be assumed (with low accuracy) to have severe hypoxaemia
- If $\text{SpO}_2 < 40\%$, the value will be considered spurious (e.g. due to incorrect data entry) and treated as not available, i.e. the child will be assumed normoxaemic.

Additionally, a description of SpO₂ values distribution will be provided based on the following cut-offs:

- $95\% \leq \text{SpO}_2 < 100\%$
- $94\% \leq \text{SpO}_2 < 95\%$
- $92\% \leq \text{SpO}_2 < 94\%$
- $90\% \leq \text{SpO}_2 < 92\%$
- $70\% \leq \text{SpO}_2 < 90\%$ (severe hypoxaemia, accuracy)
- $40\% \leq \text{SpO}_2 < 70\%$ (severe hypoxaemia, but low accuracy)
- Spurious ($0\% \leq \text{SpO}_2 < 40\%$)
- Missing

In India, where three SpO₂ measures were collected, only the first one will be used.

Mild hypoxaemia

$92\% \leq \text{SpO}_2 < 94\%$

Moderate hypoxaemia

$90\% \leq \text{SpO}_2 < 92\%$

Severe hypoxaemia

$\text{SpO}_2 < 90\%$

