6.2.4 Pre-planned Sensitivity Analyses

Sensitivity analyses on the primary outcomes are planned and will be conducted:

- ξ On first encounters, which will include only the first enrolment episode of each child during the study period (as some children may attend the facility on more than one occasion). Separate presentations are identifiable from Day0 form as the caregiver is asked whether the child attended previously and within 28 days. This is the minimum number of days required for the disease episode to be considered a new one and not a repeat visit.
- ξ Looking at different hospitalisation appropriateness (based on different definitions of primary and secondary hospitalisations). Same day (Day0), 3 days and 7 days from Day0 will be used as cut-offs for different primary and secondary hospitalisation definitions.
- ξ Looking at different referral definitions:
 - ο A child will be considered to be referred if, at Day0, caregiver confirms that the child was urgently referred *and* the research assistant confirms that an urgent referral advice was recorded for the child².
 - ο A child will be considered to be referred if, at Day0, the research assistant confirms that an urgent referral advice was recorded for the child. If urgency is unknown, referral will be assumed to be urgent.

Additionally, a set of sensitivity analyses on the primary outcomes shall be carried out in case of substantial missing data (e.g. >10%) to evaluate the impact of each method on the primary outcomes results and take them into account when interpreting the final analysis results. Planned methods will include:

- ξ Worst case scenario
- ξ Complete cases
- ξ Multiple imputations with chained equations [11, 12]

Details of the methods are provided in Section 6.3.

Sensitivity analyses will only be performed for the final statistical analysis and not for interim analyses and DMC reports.

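### SAP 6.1.1 narrows referral to urgent referral without declaring it, so an early admission after a documented non-urgent referral is scored as a severe complication instead of an appropriate hospitalisation

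*SAP*

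**What the plan says.** Protocol 6.4.2 uses referral without qualification in three outcomes:

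- Secondary hospitalisation, the non-fatal part of severe complication, covers delayed admissions and "any hospitalisation occurring without referral".
- The second primary outcome is "Proportion of children admitted to hospital within 24 hours of the Day 0 primary care consultation and as a result of a referral".
- A secondary outcome is "Proportion of children referred by a primary care healthcare provider to a higher level of care", which means a hospital or the inpatient part of a larger facility.

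The outcome list in SAP 3.1.4 repeats these without mentioning urgency.

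SAP 6.1.1 then says that a child is referred if "the caregiver confirms that the child was urgently referred or the research assistant confirms that an urgent referral advice was recorded for the child". It adds: "If urgency is unknown from both sources, referral will be assumed to be urgent". A footnote gives a different source for one country: "For India, urgent referrals will be defined based on the registry alone".

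Section 6.1 presents these general definitions as applying to several outcomes. For severe complication, SAP 6.1.2.1 states: "Hospitalisation will be counted in the numerator if the child was not referred at Day0". For appropriate hospitalisation, SAP 6.1.2.3 refers back to the 6.1.1 definition and requires admission by the end of the next day.

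SAP 6.2.4 plans two alternative referral definitions. One requires urgency from both the caregiver and the record. The other uses the record alone, with this rule: "If urgency is unknown, referral will be assumed to be urgent". SAP 1.1 claims compliance with the protocol unless a difference is detailed. The urgency condition is spelled out but not identified as a difference, and no reason is given.

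**The concern.** The same referral variable decides which primary outcome an early admission belongs to. Under the protocol, a child who was referred and admitted within a day is the result the intervention aims for. Under the SAP, if that referral was documented as non-urgent, the child becomes a failure of care: the admission counts as unreferred. One child leaves the numerator of the second primary outcome and enters the numerator of the first.

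The same child also disappears from the secondary outcomes on referral and completed referral (SAP 6.1.2.5 and 6.1.2.6). The child is added to the secondary hospitalisations reported as harms (SAP 6.5).

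The rule is also uneven. A referral with no urgency recorded anywhere counts, while one clearly documented as non-urgent does not.

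**Working it through.** **Step 1. Trace the cases.** SAP 6.1.1 operationalises 24 hours as admission on Day 0 or the next calendar day.

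| Situation | Protocol 6.4.2 | SAP 6.1.1 to 6.1.2.3 |
|---|---|---|
| Admitted Day 0/1, urgent referral confirmed by either source | appropriate hospitalisation | same |
| Admitted Day 0/1, referred, urgency unknown from both sources | appropriate hospitalisation | same |
| Admitted Day 0/1, referral documented as non-urgent, neither source confirming urgency | appropriate hospitalisation | severe complication; not appropriate hospitalisation |
| Admitted Day 0/1, no referral | severe complication | same |
| Admitted after Day 1, by Day 7 | severe complication | same |

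Only the third row changes class. SAP 6.1.2.1 does not itself refer back to the 6.1.1 definition. If it were read with the ordinary meaning of referral, the third-row child would drop out of both outcomes, which is still not what the protocol says.

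**Step 2. Look for an analysis on the protocol's definition.** The first alternative in 6.2.4 is stricter on urgency. The second changes the source and keeps the urgency condition. The other hospitalisation analyses change the cut-off day only. None uses any referral.

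**Step 3. Reproduce the planning figures.** Inputs (Protocol 6.6.1, SAP 3.4): power 80%, alpha 0.05 (taken as two-sided), ICC 0.001, severe complication 1.1% to 0.77%, appropriate hospitalisation 1.5% to 1.95% (1.5% × 1.3).

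n = [1.96·√(2·p̄·(1−p̄)) + 0.8416·√(p₁(1−p₁) + p₂(1−p₂))]² / (p₁−p₂)²

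- Severe complication: n = 13,351 per arm. Appropriate hospitalisation: n = 13,141.
- Tanzania: design effect 1 + 1679 × 0.001 = 2.679. Clusters 13,351 × 2.679 / 1680 = 21.3, rounded up to the stated 22. For the second outcome, 21.0.
- India (initial plan): design effect 1 + 509 × 0.001 = 1.509. Clusters 13,351 × 1.509 / 510 = 39.5, rounded up to the stated 40. For the second outcome, 38.9.

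The stated cluster numbers are reproduced and are not in dispute.

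**Step 4. Illustrate the size.** Let f be the share of referred Day 0/1 admissions that fall in the third row. The documents give no value, so f is an assumption, set equal in both arms. With s the severe-complication rate and h the appropriate-hospitalisation rate:

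scored severe complication = s + f·h; scored appropriate hospitalisation = h·(1 − f)

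At f = 10%: 1.1 + 0.15 = 1.25% v 0.77 + 0.195 = 0.965%, ratio 0.77. The second outcome becomes 1.35% v 1.755%, ratio 1.30.

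| f (assumed) | Severe complication, control v intervention | Ratio | Tanzania power | Appropriate hospitalisation | Ratio | Tanzania power |
|---|---|---|---|---|---|---|
| 0 | 1.10% v 0.77% | 0.70 | 81% | 1.50% v 1.95% | 1.30 | 82% |
| 5% | 1.175% v 0.868% | 0.74 | 72% | 1.425% v 1.853% | 1.30 | 80% |
| 10% | 1.25% v 0.965% | 0.77 | 62% | 1.35% v 1.755% | 1.30 | 78% |
| 20% | 1.40% v 1.16% | 0.83 | 43% | 1.20% v 1.56% | 1.30 | 73% |

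Power is at alpha 0.05, matching the plan's own calculation. In India with 60 clusters per arm, power for severe complication would go from 93.2% to 86.9%, 78.3% and 57.5% at the same values of f.

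If the intervention raised referred admissions by 30% but left true complications at 1.1% in both arms, f = 10% would give 1.25% v 1.295%, a ratio of 1.04. At 5% and 20% the ratios are 1.02 and 1.06.

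**Limits.** The calculation takes the planning rates as any-referral rates. The 1.5% came from facility staff estimates with no referral definition stated. Reclassified children who also died by Day 7 are already in the first outcome, so the figures slightly overstate the shift.

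**The case against.** The best defence is that the protocol never defines referral operationally, leaves statistical detail to the SAP, and describes the second outcome as a proxy for appropriate referral of children with severe disease. Reading that as urgent referral is a reasonable choice, and the SAP prints its definition in full. The rule is also inclusive: either source is enough, and unknown urgency counts. The affected group may be close to empty.

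Much of this stands. The group is narrow and its size unknown. Whether urgent-only captures appropriate referral better is arguable for the second outcome. It does not carry over to the first, because a child with a documented referral is not unreferred, whatever the urgency. The protocol also chose admission as its marker of severity because primary care classification is inadequate, and an urgency condition brings back a provider's judgement.

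A reader might infer three stronger points that the documents do not support:

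- **Bias between arms.** Nothing shows that arms record urgency differently. Protocol 8.1.1 describes extraction of referral advice from records, with clarification from the provider where unclear. Any split of f by arm is purely hypothetical.
- **Both treatment effects diluted.** With equal shares, the second outcome's ratio stays at 1.30 and only its power falls slightly.
- **A pooled analysis on incompatible measures.** The country difference is disclosed, each country is also analysed separately, and the record-only alternative in SAP 6.2.4 uses the same source in both.

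**Conclusion.** The point holds as an undeclared narrowing of a definition that feeds both primary outcomes. It reverses the classification of one identifiable group: children admitted on Day 0 or Day 1 after a referral documented as non-urgent, with urgency confirmed by neither source. No planned analysis would reveal its effect.

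The size cannot be stated. Under equal assumed shares of 5% to 20%, the severe-complication ratio would move from 0.70 to between 0.74 and 0.83; if the share is near zero, the effect is negligible. Those figures rest on the plan's own rates being any-referral rates and on its 30% effects being true. The severity is moderate: the text is clear and the correction cheap, but neither the frequency of the problem nor any difference between arms is documented.

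**What to change.** **Preferred.** In SAP 6.1.1, define referral for 6.1.2.1, 6.1.2.2, 6.1.2.3, 6.1.2.5 and 6.1.2.6 as any Day 0 referral advice to a hospital or inpatient unit, from caregiver report or record and regardless of urgency, as in Protocol 6.4.2. Move the urgent-only definition to the sensitivity analyses in 6.2.4.

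**Minimum, if urgent-only is kept.**

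- Do not count a documented non-urgent referral as unreferred in the severe-complication outcomes.
- Declare the urgency condition as a departure from the protocol, with its rationale, before unblinding.
- Add an any-referral sensitivity analysis of both primary outcomes.
- Report by arm and country how many Day 0/1 admissions change class.

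**Cost.** SAP wording and one extra analysis. The SAP's definitions imply that referral and urgency are already recorded, so no new data should be needed. The downside of the preferred option is small: a few non-urgent referrals admitted by the end of the next day would count as appropriate hospitalisations.
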